7.6.6 Neurological Impairment Score

Clinical activity will be assessed by a clinical assessment that tests weakness, reflexes, sensation and cranial nerves.

At each time point, 2 independent assessments will be performed. Each site will make every effort to have these assessments performed by the same Investigator. Assessments are to be performed at least 24 hours (approximately) apart from each other but not more than 7 days apart. In order to limit potential intra-operator bias, results of the first assessment will not be available to the Investigator when performing the second assessment.

7.6.7 Composite Autonomic Symptom Score

To evaluate changes in autonomic symptoms, patients will complete the COMPASS 31 questionnaire approximately once every 6 months. The COMPASS 31 questionnaire consists of 31 clinically selected questions. The questions evaluate 6 autonomic domains (orthostatic intolerance, vasomotor, secretomotor, gastrointestinal, bladder, and pupillomotor).⁵⁰

7.6.8 Quality of Life Questionnaire

Quality of life will be assessed through the use of the EQ5D-5L, a standardized 5 question instrument for use as a measure of health outcomes.

7.6.9 Rasch-built Overall Disability Scale

An assessment of the disability each patient experiences will be assessed through the R-ODS⁵¹. The R-ODS is comprised of a 24-item linearly weighted scale that specifically captures activity and social participation limitations in patients.

7.6.10 Skin Punch Biopsies for Exploratory Intraepidermal Nerve Fiber Density and Sweat Gland Nerve Fiber Density

Patients will have 2 tandem 3-mm skin punch biopsies for IENFD and SGNFD assessment obtained at Screening/Baseline and approximately once every 6 months throughout the study.

One biopsy will be taken from the distal lower leg, when a patient's clinical status allows, and one from the distal thigh at each time point.

Details of how samples will be collected, processed, and stored will be in the Study Laboratory Manual.

7.6.11 FAP Stage and PND Score

Changes in disease stage will be evaluated through FAP Stage and PND Score.^{52,53}

7.6.12 Modified Body Mass Index

The nutritional status of patients will be evaluated using the mBMI; calculated as BMI × albumin.

7.6.13 Disease Burden and Healthcare Utilization

The burden of disease and healthcare utilization will be assessed using a patient-reported 16 question pharmacoeconomics questionnaire.

7.6.14 Echocardiogram

An echocardiogram will be performed in all patients at Screening/Baseline, to assess any cardiac abnormalities. In addition, for those patients enrolled in the Cardiac subgroup, an echocardiogram will be performed during approximately once every 6 months.

7.6.15 Biomarkers of Cardiac Function

For those patients in the Cardiac subgroup, blood samples will be collected for the quantification of biomarkers of cardiac function (troponin I and NT-proBNP) prior to their first dose of study drug and approximately once every 3 months. Quantification of these biomarkers will be performed at a central laboratory.

Details of how samples will be collected, processed, and stored will be in the Study Laboratory Manual.

8 REPORTING ADVERSE EVENTS

8.1 Adverse Event Definition

An AE is any untoward medical occurrence in a patient or clinical investigational patient administered a pharmaceutical product and which does not necessarily have a causal relationship with this treatment.

An AE can therefore be any unfavorable and unintended sign (including an abnormal laboratory finding, for example), symptom, or disease temporally associated with the use of a medicinal product, whether or not considered related to the medicinal product.

8.2 Serious Adverse Event Definition

An SAE is any untoward medical occurrence that at any dose:

- Results in death;
- Is life-threatening (an event which places the patient at immediate risk of death from the event as it occurred. It does not include an event that had it occurred in a more severe form might have caused death);
- Requires inpatient hospitalization or prolongation of existing hospitalization;
- Results in persistent or significant disability/incapacity;
- Is a congenital anomaly or birth defect;
- An important medical event that may not be immediately life-threatening or result in death or hospitalization but may jeopardize the patient or may require intervention to prevent one of the other outcomes listed in the definition above (e.g., such events include allergic bronchospasm, blood dyscrasias or convulsions, or the development of drug dependency or abuse).

8.3 Eliciting Adverse Event Information

The patient should be asked about medically relevant changes in his/her health since the last visit. The patient should also be asked if he/she has been hospitalized, had any accidents, used any new medications, or changed concomitant medication routines (both prescription and OTC).

In addition to patient observations, AEs will be documented from any clinically relevant laboratory findings, physical examination findings, ECG changes, or other findings.

8.4 Adverse Event Reporting

The Investigator is responsible for reporting all AEs that are observed or reported after the first dose of study drug regardless of their relationship to study drug through the 21 or 56-day Follow-up visit (depending on whether or not the patient plans to enroll into the open-label global extension study).

Any medical condition that is present when a patient is screened and does not deteriorate should not be reported as an AE. However, if it does deteriorate at any time during the study, it should be reported as an AE.

All AEs must be fully recorded in the site's source records and in the patients' CRF, whether or not they are considered to be drug-related. Each AE should be described in

detail: onset time and date, description of event, severity, relationship to investigational product, action taken, and outcome (including time and date of resolution, if applicable).

Adverse events should be followed for the reporting periods defined earlier or until recovery to the normal state has been achieved, whichever occurs first. In the event of a patient not returning to the clinical unit, the outcome of this event will be recorded as lost at follow-up.

For patients who withdraw from the study early, ongoing AEs will be followed until resolution or 28 days from last dose, whichever occurs first.

8.5 Adverse Event Reporting Period

As stated in [Section 8.4](#), AEs will be assessed for 21 or 56 days following the last dose of study drug (depending on whether or not the patient plans to roll over to the open-label global extension study) or until recovery to the normal state has been achieved, whichever occurs first; all AEs that occur after the start of study drug administration on Day 0 (Baseline) must be reported in detail on the appropriate CRF page and followed to satisfactory resolution, or a period of 21 or 56 days after the last dose of study drug administration (depending on whether or not the patient plans to roll over to the open-label global extension study), whichever is shorter.

Serious AEs will be followed for 21 or 56 days following the last dose of study drug (depending on whether or not the patient plans to roll over to the open-label global extension study), or until satisfactory resolution, or until the SAE is considered by the Investigator to be chronic or the patient is stable, whichever occurs first.

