	Study Day	D378 & D567	D399 & D588	D420 & D609	D441 & D630	D462 & D651	D483 & D672	D504 & D693	D525 & D714	D546 & D735	D560 & D749	D756	D791	N/A	
	Window	±3D	±5D	±5D	±5D	2D to 7D									
Clinical Activity Assessments:															
mNIS + 7 ^{j,k}															
VDT ^k															
HRdb ^k															
Grip Strength ^{k,l}															
10-Meter Walk Test ^{k,m}															
NIS ^k															
Skin Punch Biopsy (IENFD & SGFND) ⁿ															
mBMI															
FAP Stage and PND Score															
COMPASS 31															
QOL and Disability Questionnaires ^o															
Premedication Administration ^p	X	X	X	X	X	X	X	X	X	X					
Study Drug Administration ^q	X	X	X	X	X	X	X	X	X	X					
Plasma PK Sampling ^r					X					X	X	X	X	X	X
Urine PK Sampling ^s					X					X	X				X

Procedure	Visit Type	Dosing										Mid-year/ Annual Efficacy Assess- ment	21- and 56-day Follow-up ^a		Early Termination
		55 & 82	58 & 85	61 & 88	64 & 91	67 & 94	70 & 97	73 & 100	76 & 103	79 & 106	81 & 108				
	Study Day	D378 & D567	D399 & D588	D420 & D609	D441 & D630	D462 & D651	D483 & D672	D504 & D693	D525 & D714	D546 & D735	D560 & D749	D756	D791	N/A	
	Window	±3D	±3D	±3D	±3D	±3D	±3D	±3D	±3D	±3D	±5D	±5D	±5D	2D to 7D	
PK/PD Subgroup Only:															
TTR (ELISA and turbidimetric)												X ^b			
RBP and Vitamin A												X ^b			
Plasma PK Sampling												X ^c			
Urine PK Sampling												X ^c			
Cardiac Subgroup Only:															
Echocardiogram												X			X
Troponin I and NT-proBNP						X					X				X
Concomitant Medications		X ^w													
Adverse Events		X ^x													

Note: The schedule of assessments for patients administered ALN-TTR02 once every 4 weeks is provided in Appendix 2.

- a If a patient enrolls in the global extension study, the patient will only have to complete the 21-day follow-up assessments (Day 756) and not the 56-day follow-up assessments (Day 791). Patients who do not enroll in the extension study will need to complete both Follow-up visits (Days 756 and 791).
- b On dosing days, weight will be measured predose.
- c On dosing days, vital signs will be measured predose. Vital signs to include: blood pressure, pulse rate, oral body temperature, and respiratory rate. Parameters are to be measured in the supine position using an automated instrument after the patient has rested comfortably for 10 minutes.
- d Triplicate recordings will be obtained.

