1.3 Summary of Clinical Data with ALN-TTR02

A Phase 1 multicenter, randomized, placebo-controlled, single-blind, single-ascending dose clinical study of ALN-TTR02 in healthy volunteers was completed in the UK. ALN-TTR02 was administered as a single 60-minute IV infusion to healthy volunteers across doses of 10 to 500 µg/kg. Patients were premedicated with dexamethasone, H1 and H2 blockers, and paracetamol prior to dosing to minimize the risk of infusion-related reactions (IRRs). Significant pharmacology in terms of TTR protein lowering (>80% reduction from pretreatment baseline) was observed at doses \geq 0.15 mg/kg. Transthyretin levels showed evidence of recovery beginning at around Day 21-28, with return to baseline by Day 70.

An open-label Phase 2 multiple ascending dose study of ALN-TTR02 in ATTR patients with FAP (Study ALN-TTR02-002) is currently enrolling patients to determine the safety and tolerability, pharmacokinetic (PK), and pharmacodynamic (PD) of a 60-70 minute IV infusion of ALN-TTR02 administered once every 3 -4 weeks for 2 doses. There have been no discontinuations or dose-limiting toxicities, and dosing is currently ongoing with the 0.3 mg/kg ALN-TTR02 dose. The preliminary PD effects on TTR are consistent with the data observed in the Phase 1 ALN-TTR02-001 study. It is anticipated that the

ALN-TTR02 dose and regimen for long-term dosing will be determined based on Study ALN-TTR02-002.

Further details on these studies can be found in the ALN-TTR02 IB.

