6.2.5 Follow-Up Visits

Patients will return to the study site for 2 follow-up visits (approximately 21 and 56 days after receiving their last dose of ALN-TTR02). If a patient enrolls in the global extension study, the patient will not have to complete the 56-day follow-up assessments. Patients who do not enroll in the extension study will need to complete both follow-up visits.

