Appropriate remedial measures should be taken by the Investigator using his/her best medical judgment to treat the SAE. These measures and the patient's response to these measures should be recorded. All SAEs, regardless of relationship to study drug, will be followed by the Investigator until satisfactory resolution or the Investigator deems the SAE to be chronic or stable. Clinical, laboratory, and diagnostic measures should be employed by the Investigator as needed to adequately determine the etiology of the event.

The Investigator will be responsible for reporting all SAEs to the local independent ethics committee (IEC) when required by national regulations.

Alnylam or its representative will be responsible for the reporting of all relevant events to the concerned regulatory authorities according to all applicable regulations.

In Europe, in accordance with the Directive 2001/20/EC, the Competent Authorities and the Ethics Committees in the concerned Member States will be notified of fatal and life-threatening Suspected Unexpected Serious Adverse Reactions (SUSARs) as soon as possible but no later than 7 calendar days after Alnylam or its representative has first knowledge of the minimum criteria for expedited reporting. Non-fatal and non-life-threatening SUSARs should be reported no later than 15 calendar days after Alnylam or its representative has first knowledge of them.

The Investigator may be informed by Alnylam or its representative of SAEs from other Investigators or clinical studies which may have relevance to this clinical trial. These SAEs should also be reported promptly to the IEC or Clinical Events Committee (CEC) that approved the study. All SAE reports should be transmitted to the IEC/CEC with a cover letter or transmittal form, and a copy of that transmittal should be maintained in the Investigator's files and forwarded to Alnylam as part of the Trial Master File on study completion.

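### Protocol 8.5 puts a 21- or 56-day limit on SAE follow-up, 8.11 sets no limit, and 8.4 adds 28 days for early withdrawals without saying whether SAEs are exempt

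*Protocol*

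**What the plan says.** Three sections of the protocol set how long an event is followed.

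- **Section 8.5, SAEs.** "Serious AEs will be followed for 21 or 56 days following the last dose of study drug", with the choice of 21 or 56 days set by roll-over to the global extension study. The sentence then adds resolution and ends "or until the SAE is considered by the Investigator to be chronic or the patient is stable, whichever occurs first". The day limit is therefore one of the alternatives, and the earliest applies.
- **Section 8.11, SAEs.** Every SAE, related or not, "will be followed by the Investigator until satisfactory resolution or the Investigator deems the SAE to be chronic or stable". No number of days is given.
- **Section 8.4, early withdrawals.** For these patients, "ongoing AEs will be followed until resolution or 28 days from last dose, whichever occurs first". The sentence speaks of AEs in general and neither includes nor exempts SAEs.

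Two further points bear on the same windows. Sections 8.4 and 8.5 and footnotes w and x of Table 1-2 let the choice of 21 or 56 days depend on what the patient intends to do. Section 6.2.5 makes it depend on what the patient does: "If a patient enrolls in the global extension study, the patient will not have to complete the 56-day follow-up assessments". Footnote a of Table 1-2 agrees with Section 6.2.5. SAP Section 4.6.2 counts new-onset events as treatment-emergent up to 28 days after the last dose and attributes that definition to the protocol.

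**The concern.** The same SAE has up to three different end points for follow-up, and the protocol gives no order of precedence. A site that works from 8.5 may stop following an SAE that is neither resolved nor stable. A site that works from 8.11 may not. For a patient withdrawn because of an SAE, which Section 4.5.1 lists as a reason for withdrawal, the 28-day sentence in 8.4 also comes into play. Section 4.5.2 does not settle the matter, because it refers back to the safety follow-up that the protocol specifies elsewhere.

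Safety is the primary objective and at most 28 patients are expected. In a study of that size, one serious event whose final outcome is unknown is noticeable. Whether that outcome is known should not depend on which section a site happened to read.

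**Working it through.** **1. The plan's own days.** On the every-3-week schedule the last dose is on Day 735 (Table 1-2). Then 735 + 21 = 756 and 735 + 56 = 791, which are the two follow-up visit days in the table.

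**2. The limits in order.**

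- 8.5, patients rolling over: 21 days
- 8.4, ongoing AEs in early withdrawals: 28 days
- 8.5, patients not rolling over: 56 days
- 8.11, all SAEs: no limit

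The early-withdrawal limit is 28 − 21 = 7 days longer than the roll-over limit and 56 − 28 = 28 days shorter than the limit for completers who do not roll over (28/56 = one half).

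**3. One event under each rule.** Take an SAE that starts 20 days after the last dose and stays unresolved and unstable.

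| Rule | Follow-up of the event |
|---|---|
| 8.5, rolling over | 21 − 20 = 1 day |
| 8.4, early withdrawal, if it covers SAEs | 28 − 20 = 8 days |
| 8.5, not rolling over | 56 − 20 = 36 days |
| 8.11 | until resolved, chronic or stable |

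The first three rows can end before the final outcome is known. The last cannot.

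**4. A comparison inside the protocol.** Footnote c of Table 1-1 follows AEs that are ongoing from the parent study on Day 0 until they resolve, with no day limit. Read with 8.5, a carried-over non-serious AE can be followed for longer than a new SAE on study drug.

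**5. Intention against enrolment.** A patient who intends to roll over but does not enter has a 21-day window under 8.4 and 8.5 and a 56-day window under 6.2.5. The two differ by 56 − 21 = 35 days (Days 22 to 56 after the last dose).

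**6. The SAP window.** The protocol collects AEs to 21 or 56 days, and the SAP counts new-onset events to 28 days. For roll-over patients the SAP window runs 28 − 21 = 7 days past collection. For the others, collection runs 56 − 28 = 28 days past the window. The only 28-day figure in protocol Section 8 is the follow-up limit for early withdrawals in 8.4, which is not a definition of treatment-emergent.

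**The case against.** Several stronger conclusions are tempting, and the case against them is sound.

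- **That follow-up ends soonest in patients who stop early.** A reader might infer this from the 28-day sentence. It is wrong: the shortest limit is 21 days, for roll-over patients. Early withdrawals may be more exposed in practice because they enter no further study, but the protocol does not say whether ongoing events are carried into the extension, so neither group's actual loss can be established.
- **That events are closed with no outcome.** Section 8.9 provides codes for ongoing and lost to follow-up. What can be missing is the final outcome.
- **That the safety results are biased in the drug's favour.** SAP Section 4.6.2 tabulates incidence, maximum severity and maximum relationship. It plans no summary of duration or outcome, and a known SAE stays in the count.
- **That 35 days of AE capture are lost.** This is not automatic. Under 6.2.5 and footnote a, a patient who does not enrol still owes the Day 791 visit, and Section 8.3 asks about health since the last visit. Of Days 22 to 56, only Days 22 to 28 could add new-onset events to the SAP's treatment-emergent tables.
- **That the windows are too short for the drug's effect.** Section 1.3 reports that "Transthyretin levels showed evidence of recovery beginning at around Day 21-28, with return to baseline by Day 70". Those are single-dose data in healthy volunteers, and no passage links the AE windows to TTR recovery.

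It can also be said that 8.11 covers all SAEs and so overrides the 28 days in 8.4. That is a reasonable reading, but 8.4 does not state it, and it does not remove the conflict between 8.5 and 8.11.

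**Conclusion.** The contradiction between 8.5 and 8.11 is on the page, and 8.4 leaves open whether its 28-day limit reaches SAEs. Under 8.4 or 8.5 an unresolved, unstable SAE can stop being followed before its final outcome is known; under 8.11 it cannot. For an SAE that starts 20 days after the last dose, the permitted follow-up ranges from 1 day to no limit.

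The consequence is limited to final outcome and duration. Incidence is not affected, because known SAEs are still counted, and the documents do not support a claim of favourable bias. How many events would be affected cannot be derived from the documents. The day counts assume the every-3-week schedule, which is the one described in SAP Section 1.2.1. The early-withdrawal row assumes that 8.4 covers SAEs, which rests only on the absence of an exemption.

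The mismatch between intended and actual roll-over, and the SAP's 28-day window, are smaller drafting inconsistencies that belong in the same correction.

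**What to change.** Reconcile 8.4, 8.5 and 8.11 into one rule.

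1. In 8.5, remove the 21- or 56-day limit from the SAE sentence, so that it agrees with 8.11.
2. In 8.4, state that the 28-day limit for early withdrawals does not apply to SAEs.
3. In 8.4, 8.5 and footnotes w and x of Table 1-2, make the choice of 21 or 56 days depend on actual enrolment in the extension study, as 6.2.5 and footnote a already do. The SAP reproduces Table 1-2 and should carry the same change.
4. Align the 28-day treatment-emergent window in SAP Section 4.6.2 with the protocol's 21- or 56-day AE collection, and correct the statement that the definition comes from the protocol.

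Extending AE follow-up of early withdrawals to 56 days, or ending collection at the first extension-study dose, would be separate design choices. Neither is needed to remove the conflict.

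The cost is a wording change in both documents and a few SAE records that stay open longer.

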8.6 Assessment of Causality

Causal relationship assessment to drug treatments is required for purposes of reporting AEs. To promote consistency, the following guidelines should be taken into consideration along with good clinical and scientific judgment when determining the relationship of drug treatments to an AE:

Definitely Related: A clinical event, including laboratory test abnormality, occurring in a plausible time relationship to the medication administration, and which cannot be explained by concurrent disease or other drugs or chemicals. The response to withdrawal of the drug should be clinically plausible.

Possibly Related: A clinical event, including laboratory test abnormality, with a reasonable time sequence to the medication administration, but which could also be explained by concurrent disease or other drugs or chemicals. Information on the drug withdrawal may be lacking or unclear.

Unlikely Related: A clinical event, including laboratory test abnormality, with little or no temporal relationship to medication administration, and which other drugs, chemicals, or underlying disease provide plausible explanations.

Not Related: A clinical event, including laboratory test abnormality, that has no temporal relationship to the medication or has more likely alternative etiology.

8.7 Assessment of Severity

Adverse events are to be graded according to the categories detailed below.

Mild: Mild events are those which are easily tolerated with no disruption of normal daily activity.

Moderate: Moderate events are those which cause sufficient discomfort to interfere with daily activity.

Severe: Severe events are those which incapacitate and prevent usual activity.

Changes in severity should be documented in the medical record to allow assessment of the duration of the event at each level of severity. Adverse events characterized as intermittent require documentation of the start and stop of each incidence. When changes in the severity of an AE occur more frequently than once a day, the maximum severity for the experience that day should be noted. If the severity category changes over a number of days, then those changes should be recorded separately (with distinct onset dates).

